3.5. Determination of Sample Size

A post hoc analysis was conducted using a subgroup of AUX-CC-871 subjects who were rated with moderate/severe AC based on baseline MRI images. This subgroup displayed a notable treatment effect (EN3835 vs placebo) on the pain and composite components of the adapted ASES questionnaire. This subgroup also displayed a treatment effect trend for the functional component of the adapted ASES. Given this result, the sample size calculation is based on the mean and SD found in this subgroup for the adapted ASES composite score on Day 95. Given a mean change from baseline value in adapted ASES composite score at Day 95 of 38.6 for the EN3835 group and 27.6 for the placebo group with an SD of 21.6, a sample size of approximately 142 subjects would be required given a 1:1 randomization and a type I error of

0.05 with a power of 85%. With an expected drop-out rate of approximately 20%, 180 subjects (90 EN3835 and 90 placebo) should be dosed to ensure 142 complete the study.

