4.8.1.2. Intensity of Adverse Events

Intensity (or severity) of AEs will be graded as "Mild", "Moderate" or "Severe". For AEs with missing severity, the most severe assessment will be imputed for analyses as "Severe", following worst case principle.

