7.10.2. Adverse Events

Proportion of subjects reporting at least 1 adverse event, treatment-emergent adverse event, adverse event of special interest, and serious adverse event will be compared for EN3835 to placebo treatment group using Fisher's exact test.

The null and alternative hypotheses for this test will be as below:

 H_0 : p1 = p2 (Proportion of subjects having an adverse event are equal in treatment groups) Vs

H₁: $p1 \neq p2$ (Proportion of subjects having an adverse event are unequal in treatment groups) Where,

p1: Proportion of subjects having adverse event in EN3835 treatment group.

p2: Proportion of subjects having adverse event in placebo treatment group.

Number and proportion of subjects with at least 1 adverse event, treatment-emergent adverse event, adverse event of special interest, and serious adverse will be summarized by treatment groups and in addition p value for treatment comparison will also be presented.

All AE summary tables will include only TEAEs, unless otherwise specified.

AEs will be summarized by SOC and PT. A subject will only be counted once per SOC and PT.

For AEs by severity grade (mild, moderate, severe), if a subject has multiple events occurring in the same SOC or same PT, then the event with the maximum intensity (ie, severe) will be counted.

For AEs by relationship to study drug, if a subject has multiple events occurring in the same SOC or same PT, the event with the highest association (ie, related) to study drug will be summarized.

AEs will be presented in decreasing order of the incidences at SOC level and within each SOC, in decreasing order of the incidences at the PT level.

An overall summary of AEs and AEs related to study drug will be presented and will include:

- Total number of TEAEs reported.
- Total number of TEAEs reported by severity.
- Total number of TEAEs of special interest.
- Subjects with any TEAE.
- Subjects with any TEAE of special interest.
- Subjects with any serious TEAE.
- Subjects with any severe TEAE.
- Subjects with no severe TEAEs, but at least 1 moderate TEAE.
- Subjects with no severe TEAEs, but at least 1 mild TEAE.
- Subjects with any TEAEs leading to drug interruption/withdrawal.
- Subjects with any TEAEs leading to study discontinuation.
- Subjects with any TEAEs resulting in death.

The following summary tables will be presented by SOC and PT:

- All TEAEs.
- Study drug related TEAEs.
- TEAEs by severity.
- Study drug related TEAEs by severity.

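### The mild row of the overall adverse event summary does not exclude moderate events, so some subjects fall in two severity rows

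*SAP*

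**What the plan says.** SAP section 7.10.2 describes an overall summary of adverse events, given once for all TEAEs and once for those related to study drug. It includes a total row, "Subjects with any TEAE", and three consecutive subject-level severity rows:

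- The severe row is labelled "Subjects with any severe TEAE".
- The moderate row, which comes next, is labelled "Subjects with no severe TEAEs, but at least 1 moderate TEAE".
- The mild row, which closes the group, is labelled "Subjects with no severe TEAEs, but at least 1 mild TEAE".

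SAP section 4.8.1.2 uses three grades (mild, moderate, severe) and imputes a missing grade as severe, as does section 6.3. Every TEAE therefore carries a grade.

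For the severity tables by system organ class and preferred term, section 7.10.2 has a separate rule for a subject with several events in the same SOC or PT: "then the event with the maximum intensity (ie, severe) will be counted". Table layouts are in SAP Module 2, which is not among the documents.

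**The concern.** The moderate row removes subjects who have an event of the grade above. The mild row should do the same for both grades above it, but it removes only subjects with severe events. As defined, it is neither a count of subjects with any mild TEAE (subjects with severe events are dropped) nor a count of subjects whose worst TEAE is mild (subjects with moderate events are kept).

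A reader of the summary will probably take the three rows as a split by worst grade and the last row as the subjects with mild events only. On that reading the mild row is too high. The three rows also will not add up to the any-TEAE row, which invites queries about a table that is otherwise sound.

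**Working it through.** The plan gives no figure for this row, so there is none to reproduce. The check is of the counting rule, followed by an illustration of size.

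**Step 1. All severity patterns.** With three grades and no ungraded events, a subject with at least one TEAE has one of seven patterns. Applying the row definitions as written:

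| Severe | Moderate | Mild | Rows entered as written | Rows entered if moderate is also excluded |
|---|---|---|---|---|
| no | no | yes | mild | mild |
| no | yes | no | moderate | moderate |
| no | yes | yes | **moderate and mild** | moderate |
| yes | no | no | severe | severe |
| yes | no | yes | severe | severe |
| yes | yes | no | severe | severe |
| yes | yes | yes | severe | severe |

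Six patterns enter one row and one enters two. Let *k* be the number of subjects with moderate and mild but no severe TEAEs. Then:

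- mild row = (subjects whose worst TEAE is mild) + *k*
- severe + moderate + mild rows = (subjects with any TEAE) + *k*

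This needs no data. With the exclusion extended to moderate events, each pattern enters exactly one row and the rows sum to the any-TEAE count.

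**Step 2. Illustration of *k*.** The planned number dosed is 90 per arm (SAP section 3.5). The rates below are assumptions and appear nowhere in the documents: 3% of subjects with any severe, 20% with any moderate and 60% with any mild TEAE, independent of one another.

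- Severe row: 90 × 0.03 = 2.7
- Moderate row: 90 × 0.97 × 0.20 = 17.5
- Mild row as written: 90 × 0.97 × 0.60 = 52.4
- Mild as worst grade: 90 × 0.97 × 0.80 × 0.60 = 41.9
- Excess *k*: 90 × 0.97 × 0.20 × 0.60 = 10.5
- Any TEAE: 90 × (1 − 0.97 × 0.80 × 0.40) = 62.1
- Sum of the three rows as written: 2.7 + 17.46 + 52.38 = 72.5, which is 10.5 above 62.1

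**Step 3. Range.** Keep 3% severe and independence, and let any-moderate run from 10% to 40% and any-mild from 40% to 80%. The excess then runs from 90 × 0.97 × 0.10 × 0.40 = 3.5 to 90 × 0.97 × 0.40 × 0.80 = 27.9 subjects per arm. Independence between moderate and mild events matters too. At the Step 2 rates, without it, *k* could lie anywhere from 0 (no subject without severe events has both grades) to 17.5 (every subject in the moderate row also has a mild event).

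**The case against.** The best defence is that the SAP never says the three rows are mutually exclusive, show worst grade, or sum to the any-TEAE row. The same list holds other overlapping subject rows, such as serious TEAEs and TEAEs leading to discontinuation. A count that matches its own label is not a wrong count. The number a reader wants can also be recovered: any TEAE minus the severe row minus the moderate row gives the mild-as-worst count (62.06 − 2.70 − 17.46 = 41.9 in the illustration). And the shells in Module 2 may word the row differently.

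Much of this stands, and it limits the point to one descriptive row. It does not remove it. Excluding severe events from the moderate and mild rows makes sense only as a split by worst grade, no passage says the overlap is deliberate, and the mild row answers no natural question as it stands. If the shells are right, the SAP text should still match them.

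Two stronger readings are tempting, and the documents support neither.

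- A reader might infer a contradiction with the maximum-intensity rule in the same section. That rule covers multiple events within one SOC or PT and governs different tables. It does not conflict with this row, and it does not repair it.
- A reader might infer that the excess is larger in the EN3835 arm, from the local-reaction rates of the earlier study AUX-CC-871 in Protocol section 2.3. Those seven rates sum to 34.2 + 28.7 + 21.1 + 19.8 + 19.4 + 8.0 + 5.1 = 136.3%, so an average of about 1.36 of these related terms per subject. But the section gives no placebo rates and no severity split, so it does not show how often moderate and mild events occur together, or in which arm.

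**Conclusion.** The point holds as a minor error in a row definition. Followed as written, SAP section 7.10.2 counts subjects with both moderate and mild (and no severe) TEAEs in two rows. The mild row and the sum of the three rows are each too high by the number of such subjects, relative to a worst-grade split. That the split is by worst grade is an inference from the severe and moderate rows; the SAP does not state it.

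The size is unknown. The 10.5 subjects per arm, and the range of 3.5 to 27.9, rest entirely on assumed rates and independence. No direction between arms can be claimed.

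It would be too much to say that the safety results as a whole are misstated. Fisher's exact tests in this section compare subjects with any AE, TEAE, AESI or SAE and do not use the severity rows. The severe, moderate and any-TEAE rows, the totals of events by severity, the SOC and PT severity tables and the listings are unaffected. The damage is confined to one descriptive row, which appears in both the all-TEAE and the related-TEAE versions of the summary.

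**What to change.** In the mild row of SAP section 7.10.2, insert *or moderate* after *severe*, so that the row counts subjects with at least one mild TEAE and none of a higher grade. Apply this to both the all-TEAE and the related-TEAE versions. Check the shells in SAP Module 2 and align them if they carry the same wording. The three rows then partition the subjects with any TEAE, which also gives the programmer a simple check on the table.

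The cost is two words in the SAP and a matching edit to the shells where needed. No data collection, test or other table changes.

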7.10.3. Clinical Laboratory

Student *t* test (2-sample *t* test) will be used to compare EN3835 to placebo for change from baseline in the laboratory parameters (hematology and chemistry) at the Day 95 Visit.

The null and alternative hypotheses for this test will be as below:

H₀: There is no significant difference in mean change in laboratory parameters for 2 treatment groups.

Vs

H₁: There is significant difference in mean change in laboratory parameters for 2 treatment groups.

Hematology and chemistry results will be summarized by each treatment group using descriptive statistics for observed and change from baseline values along with p value at Day 95/EOS Visit.

Proportion of subjects reporting with PCI laboratory values will be compared for EN3835 to the placebo treatment group using Fisher's exact test. Refer to Table 13 for PCI criteria.

The null and alternative hypotheses for this test will be as below:

 H_0 : p1 = p2 (Proportion of subjects having PCI laboratory values are equal in treatment groups)

Vs

 H_1 : p1 \neq p2 (Proportion of subjects having PCI laboratory values are unequal in treatment groups)

Where,

p1: Proportion of subjects having PCI laboratory values in EN3835 treatment group.

P2: Proportion of subjects having PCI laboratory values in placebo treatment group.

The PCI laboratory values will be summarized by treatment groups. In addition, the p value for treatment comparison will be presented.

A subject listing will be presented for all laboratory parameters (hematology, biochemistry, urinalysis, TSH and HbA1c). Serum and urine pregnancy test results will be listed separately.

7.10.4. Vital Signs

Student *t* test (2-sample *t* test) will be used to compare EN3835 to placebo for change from baseline in the vital signs (SBP, DBP, pulse rate, respiratory rate, body temperature, and body weight) at Day 1, 22, 43, 64, and 95 Visits.

The null and alternative hypotheses for this test will be as below:

H₀: There is no significant difference in mean change in vital sign parameters between the 2 treatment groups.

Vs

H₁: There is a significant difference in mean change in vital sign parameters between the 2 treatment groups.

Vital signs (SBP, DBP, pulse rate, respiratory rate, body temperature) taken on the injection days will be summarized across the required measurement time points (15 minutes and 30 minutes post injection) for each treatment group using descriptive statistics for observed and change from baseline values.

Vital signs taken at each visit will be summarized across study visits not including the post injection time points for each treatment group and overall using descriptive statistics for observed and change from baseline values along with *p* value.

Proportion of subjects reporting with PCI vital sign values will be compared for EN3835 to the placebo treatment group using Fisher's exact test. Refer to Table 14 for PCI criteria.

The null and alternative hypotheses for this test will be as below:

 H_0 : p1 = p2 (Proportion of subjects having PCI vital sign values are equal in treatment groups)

Vs

 H_1 : $p1 \neq p2$ (Proportion of subjects having PCI vital sign values are unequal in treatment groups)

Where,

p1: Proportion of subjects having PCI vital sign values in EN3835 treatment group.

p2: Proportion of subjects having PCI vital sign values in placebo treatment group.

The PCI vital sign values will be summarized by treatment groups. In addition, the p value for treatment comparison will be presented.

A listing will be presented for vital signs results.

7.10.5. 12-Lead ECG

The investigator interpretation of ECG results (normal, abnormal not clinically significant, or abnormal clinically significant) will be summarized by each treatment group and overall using frequency counts and percentages.

A listing of investigator interpretation of ECG results will be presented.

7.10.6. Physical Examination

Physical examination results (by body system) at baseline and at Day 95/ET will be presented by each treatment group and overall using frequency counts and percentages.

A listing will be presented for the physical examination results (by body system).

7.10.7. Immunogenicity

The immunogenicity analysis of binding and neutralizing anti-AUX-I and anti-AUX-II antibodies will be summarized by the number of subjects with an immunogenicity sample, the percentage of subjects with a positive sample, and the average titer level of the positive samples at Screening and Day 95/ET along with summary statistics if antibody assays are conducted.

The titer levels will be logarithmically transformed prior to being summarized. Samples from Screening and Day 95/ET will be analyzed for anti-AUX-I and anti-AUX-II antibodies and only positive samples will be analyzed for neutralizing antibodies. Neutralizing antibody results will be summarized as percentage of samples tested by positive/negative results.

A listing of immunogenicity results by subject will be provided.

7.11. Other Analyses

7.11.1. X-Ray

A listing for x-ray will be provided.

7.11.2. Physical Therapy

A listing for physical therapy will be provided.

7.11.3. Home Exercise

The compliance of home exercises at all study days (starting 3 days after each study treatment up to the Day 95/ET Visit) will be summarized for each treatment group and overall using descriptive statistics.

A listing for home exercise will be provided.

8. CHANGE FROM PROTOCOL

This SAP is prepared based on the study protocol; original version dated April 06, 2020, Amendment 1 dated July 10, 2020, Amendment 2 dated July 31, 2020, Amendment 3 on November 06, 2020, and Amendment 4 on October 22, 2021.

Table 17 lists any significant changes in the SAP from what is proposed in the protocol.

Text in Protocol	Change in SAP	Justification
The Per-Protocol (PP) Population is defined as those subjects in the mITT Population who do not have any major protocol deviations.	The PP Population is defined as those subjects in the mITT Population who do not have any major protocol deviations which have a significant effect on the primary endpoint.	Change the PP Population to emphasize only subjects with major PDs that effect the primary endpoint to be excluded. This allows subjects with major PDs related to safety only (and no effect on primary endpoint) to be included in PP Population.
N/A	Added a tipping point sensitivity analysis (section 7.9.4)	Tipping point analysis checks if the missing data effects the primary analysis conclusions by checking severity of missing data. Identify the tipping poing where treatment effect in subjects with missing data overturns the significant treatment effect otbtained in the missing at random primary analysis.

Table 17:Changes from Protocol

9. **REVISION HISTORY**

Non-editorial changes made to any of the modules of this SAP will be recorded in Table 18.

Table 18:Revision History

Version	Date	Revision Author	Comments
v1.0	Aug 12, 2020		Original version
v2.0	April 25, 2022		Protocol amendment updates, prior/concomitant definition, adverse events of special interest, tipping point sensitivity analysis

11. TABLES, LISTINGS, AND GRAPH SHELLS

The layouts of the summary tables, subject listings, and graphs are presented in SAP Module 2. These layouts incorporate all the appropriate table titles, table numbers, and footnotes.
